2.3.2.3 Immunogenicity

Immunogenicity of Adalimumab as determined by the formation of anti-drug-antibodies (ADAs) will be assessed by using validated immunoassays. Immunogenicity data will be received as external source data for analysis.

Blood samples for immunogenicity (assessment of anti-adalimumab antibodies development) will be taken at specified time points as indicated in [Table 2-5](#)

Table 2-5 Blood collection schedule for ADA and PK samples

Study visits	Time/Week
Visit 2	Baseline
Visit 3	Week 2
Visit 4	Week 4
Visit 8	Week 12
Visit 14	Week 24
Visit 15	Week 36
Visit 16	Week 48
End of Study Visit	If applicable
Unscheduled Visit	If applicable

All samples were analyzed in a screening assay. Study samples with a result below the validated screening cut-point were negative for binding anti-adalimumab antibodies and will be reported accordingly. In the event of a positive result (result above the screening cut-point) the sample were additionally analyzed in a secondary confirmatory assay (specificity assay). In case the assay signal could be reduced after addition of excess of adalimumab beyond the validated confirmatory cut-point, a sample was reported as confirmed binding positive. In contrast, samples with a result above the screening cut-point in the screening assay but which were negative in the confirmatory assay were reported as negative.

A transient ADA response occurs where a post baseline positive ADA response occurs but is followed by a negative ADA response before the end of Treatment Period 1 or end of study visit.

The incidence of patients with neutralizing ADAs will be summarized by treatment arms.

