4.6.3 Immunogenicity

Summary statistics (frequency and percentage) by treatment group and overall and sampling day will be provided for the percent of patients with ADA formation at baseline, weeks 2, 4, 12, 24, 36 and 48 or End of Study visit.

ADA positive patients at baseline will not be considered for the analysis of immunogenicity (development of ADA) at post-baseline assessments. A patient is considered as ADA positive during the study if the patient had at least one post baseline ADA positive sample otherwise the patient is regarded as ADA negative. Note this will also include any unscheduled visits during the Study Period.

A transient ADA response occurs where a post baseline positive ADA response occurs but is followed by a negative ADA response during the study.

The titer and the concentration of confirmed positive results will be reported. In addition, confirmed positive ADA samples will be analyzed for their neutralization potential in a neutralizing antibody (NAb) assay.

The incidence of ADA positive patients, patients with a transient response and patients with neutralizing ADAs will be summarized by treatment arms.

All ADA data will be listed (including titer and concentration).

The SAF will be used to summarize the data.

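### Transient ADA has two different time windows in the SAP, and neither requires the patient to stay or end negative, so the by-arm transient incidence is ambiguous and can include patients who are positive at their last sample.

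*SAP*

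**What the plan says.** SAP 2.3.2.3 calls an ADA response transient when a positive sample occurs after baseline "but is followed by a negative ADA response before the end of Treatment Period 1 or end of study visit". SAP 4.6.3 repeats the definition with another window: a positive sample occurs after baseline "but is followed by a negative ADA response during the study".

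The class is reported. SAP 4.6.3 states: "The incidence of ADA positive patients, patients with a transient response and patients with neutralizing ADAs will be summarized by treatment arms". It defines positivity separately: "A patient is considered as ADA positive during the study if the patient had at least one post baseline ADA positive sample", unscheduled samples included. It also plans, by treatment group, the "percent of patients with ADA formation at baseline, weeks 2, 4, 12, 24, 36 and 48 or End of Study visit", reports titers, and lists all ADA results. Patients who are ADA positive at baseline are left out of the post-baseline analysis.

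SAP 2.1.2 and 2.7 set out separate outputs for Study Period 1, Study Period 2 and the entire study. Neither ADA section says which of these the transient incidence belongs to. The protocol (6.5.6 and 9.5.4) does not define transient ADA, and neither document defines or plans a persistent category.

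**The concern.** There are two faults. First, the windows differ, and section 2.3.2.3 joins two end points with an or but gives no rule for when each applies. Two programmers could derive different transient counts from the same data.

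Second, neither wording deals with a patient who turns positive again. A patient who is positive at Week 4, negative at Week 12, and positive at Weeks 24, 36 and 48 meets both definitions because of the Week 12 sample. That patient's ADA returned and continued through Study Period 2, in which everyone receives GP2017, yet the label says that the response went away.

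ADA formation is a secondary objective in both periods, including after the switch from Humira (protocol 2.2). The transient incidence is one of three patient-level ADA summaries by arm, and the only one that describes duration.

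**Working it through.** The documents state no figure for transient ADA, so there is none to reproduce. The check applies each wording literally to every possible sequence of results.

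**Inputs.** There are six scheduled post-baseline samples, at Weeks 2, 4, 12, 24, 36 and 48 (protocol 6.5.6, SAP Table 2-5). Sequences with at least one positive: 2^6 − 1 = 63. Unscheduled and missing samples are ignored.

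**Formula.** Let the window cover the first *m* samples. Sequences with a positive followed by a negative inside the window number 2^m − 1 − m: all sequences, less the all-negative one, less the *m* that never turn negative after a positive. Multiply by 2^(6−m) for the samples outside the window.

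| Reading | m | Transient, of 63 | Of these, positive at Week 48 | Classed differently from 4.6.3 |
|---|---|---|---|---|
| 4.6.3, through Week 48 | 6 | 64 − 1 − 6 = 57 | 26 | – |
| 2.3.2.3, end of study, Week 48 included | 6 | 57 | 26 | 0 |
| 2.3.2.3, strictly before Week 48 | 5 | 26 × 2 = 52 | 26 | 5 |
| 2.3.2.3, end of Treatment Period 1, Week 24 included | 4 | 11 × 4 = 44 | 22 | 13 |
| 2.3.2.3, strictly before Week 24 | 3 | 4 × 8 = 32 | 16 | 25 |

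So section 2.3.2.3 agrees with 4.6.3 on one reading and differs on the other three.

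**Two example patients.**
- Positive at Week 12, negative at Week 24, positive at Weeks 36 and 48: transient under 4.6.3 and under the Treatment Period 1 reading with Week 24 included.
- Positive at Weeks 12 and 24, negative at Weeks 36 and 48: transient under 4.6.3, but not under the Treatment Period 1 reading.

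**Under the rule proposed below.** A transient sequence is one run of positives followed by negatives to the end, possibly after early negatives. There are m(m − 1)/2 of these.
- Entire study: 6 × 5/2 = 15. Against 4.6.3, 57 − 15 = 42 sequences move out of transient: 26 that end positive and 16 that end negative after a recurrence.
- Study Period 1 alone (four samples, 15 sequences with a positive): the current rule gives 11, of which 4 end positive. The proposed rule gives 4 × 3/2 = 6, so 5 move.

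**Illustration with assumed rates.** Take a patient positive at Week 4 whose true status stays positive, and let each later sample read negative independently with probability q. Neither q nor independence comes from the documents.
- Called transient under 4.6.3 (four later samples): 1 − (1 − q)^4, which is 18.5% at q = 5% and 34.4% at q = 10%.
- Part of this with only trailing negatives, which the proposed rule still calls transient: the sum over k = 1 to 4 of q^k (1 − q)^(4−k), which is 4.5% and 8.2%.
- Share that the rule reclassifies: 18.5 − 4.5 = 14.0% and 34.4 − 8.2 = 26.2%.
- In Study Period 1 only Weeks 12 and 24 follow, and only negative-then-positive is reclassified: 0.05 × 0.95 = 4.75% and 0.10 × 0.90 = 9%.

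**The case against.** The strongest reply is that little rests on this class. ADA-positive status needs only one post-baseline positive, so it is the same under every transient rule. By-visit rates show continuing positivity, and the listing shows each patient's full sequence. The protocol objectives concern the rate or incidence of ADA formation, and the sensitivity analyses by ADA status (SAP 4.5 and 4.6.1.1) use positive versus negative only. All of this stands, and it makes the point minor.

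It can also be said that section 2.3.2.3 is period-specific: the first end point for Study Period 1 tables, the second for the entire study. That reading is reasonable, and with Week 48 included it removes the conflict for the entire-study count. But the SAP does not say so, and the reading does nothing about patients who turn positive again.

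A reader might infer that persistent ADA is under-reported. The documents do not support this. No persistent category is defined or planned, and a persistent count would be too low only if someone derived it as ADA positive minus transient. Nor do they support an inference that GP2017 is made to look milder than Humira: the same rule applies to both arms, and the samples are analyzed blinded (protocol 6.5.6.1).

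**Conclusion.** The point holds as a minor defect in a descriptive endpoint. The windows in the two sections differ as written, and under either one a single later negative makes a patient transient, whatever follows. The transient incidence is therefore ambiguous and can include patients who are positive at their last sample.

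The direction depends on the reading. Against the proposed rule, section 4.6.3 can only overstate the transient count. The Treatment Period 1 reading can also miss patients who turn negative for good after Week 24.

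The 57 of 63 and 26 of 57 describe what the wording allows; they are not expected patient proportions. The 14% and 26% hold only for a patient positive from Week 4 and rest on assumed, independent per-sample rates. Without ADA or reversion rates in the documents, the number of patients affected and any between-arm difference cannot be computed.

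**What to change.** Put one definition in SAP 2.3.2.3 and refer to it from 4.6.3. A response is transient if the patient has at least one post-baseline positive, the last evaluable sample of the period is negative, and there is no positive after the first negative that follows the first positive. The last phrase matters: without it, a negative before ADA first appears would disqualify the patient.

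Report all other ADA-positive patients as one non-transient group. This group includes patients whose only positive is their last sample, so it should not be read as persistent.

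Apply the rule separately to Study Period 1, through Week 24, and to the entire study, through Week 48 or End of Study. Including the Week 24 sample in Study Period 1 agrees with SAP 4.1.2, which assigns assessments on the first day of Study Period 2 to Study Period 1.

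The cost is a small change in SAP wording and in one derivation, on data already collected. The transient count may be lower than under section 4.6.3.

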4.6.4 Pharmacokinetic evaluations

Through adalimumab serum concentrations at Baseline, Weeks 2, 4, 12, 24, 30, 36 and 48 or End of Study visit will be summarized with descriptive statistic by treatment group and overall. Concentrations will be listed together with ADA results.

4.7 Handing of missing data in the analysis

Refer to Section 2.3.1.1, [Appendix 1](#), and [Appendix 2](#).

5 Clinical Study Report – Appendix 16.1.9 Documentation of statistical methods

Appendix 16.1.9 of the CSR will contain the last SAP versions before database lock and the full SAS® outputs of the MMRM analyses of DAS28-CRP and DAS28-ESR as well as the ANCOVA analyses of the time-weighted averaged change from baseline approaches.

6 Appendices

6.1 Appendix 1: Adverse event partial date imputation

6.1.1 Adverse event end dates

- If the day is missing, then impute the last day of the month
- If the day and month are both missing, then impute the date with the day and month of the last available assessment date for the patient.
- If the end date is completely missing, the event will be assumed to be 'Ongoing'

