In general, for by-visit summaries, data recorded at the nominal visit will be presented. With the exclusion of AEs (see in Section 2.3.2.1), only data up to study discontinuation (i.e., including End of Study visit) will be analyzed, but all the data will be listed. End of Study visit within the nominal visit windows on a condition of absence of a nominal visit will be assigned to the nominal visit (see in Section 4.1.4), otherwise it will be included as a separate visit regardless of the day it took place. Unless otherwise noted, unscheduled visits will not be included in by-visit summaries. However unscheduled measurements will be presented in the listings.

Date imputations will be performed as described in [Appendix 1](#) and [Appendix 2](#). Imputed dates will be used for further derivations, only the not imputed partial dates will be presented in the listings.

Study Period 1 summary tables will be presented by treatment as

- GP2017
- Humira
- Total

Study Period 2 summary tables will be presented by treatment as

- Continued GP2017
- Humira to GP2017
- Total

Overall (including entire study) summary tables will be presented by treatment as

- GP2017
- Humira/Switched GP2017
- Total

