2.3.2 Safety and tolerability assessments

2.3.2.1 AEs

An adverse event is the appearance or worsening of any undesirable sign, symptom, or medical condition occurring after starting the study drug even if the event is not considered to be related to study drug. Study drug includes the investigational drug under evaluation and the comparator drug that is given during any phase of the study. Medical conditions/diseases present before starting study drug are only considered adverse events if they worsen after starting study drug. Abnormal laboratory values or test results constitute adverse events only if they induce clinical signs or symptoms, are considered clinically significant, or require therapy.

Adverse events will be coded using MedDRA version 20.0.

Treatment emergent AEs (TEAEs) are events started after the first dose of study treatment and before study discontinuation or 30 days after last dose, whichever occurs later. In case where it is not possible to define an AE as TEAE or not, the AE will be classified by the worst case, i.e. treatment emergent.

All adverse events with start date on or after the date of the first study medication in SP2 will be counted as belonging to Study Period 2. In the case of a partial start date see [Appendix 1](#) on how such cases will be handled. If it is unclear whether the AE belongs to SP1 or SP2 then the AE will be assigned to SP2. This is a conservative approach since all patients are treated with the investigational product GP2017 in SP2.

Adverse events of special interest are defined as a subset of TEAE in [Appendix 3](#).

The investigator or qualified designee will have recorded ISRs belonging to one of the following: injection site erythema, injection site haematoma, injection site induration, injection site inflammation, injection site nodule, injection site oedema, injection site pain, injection site pruritus, injection site rash or injection site discolouration at the specified time points. Incidence and occurrence of ISRs and symptoms will be calculated.

All ISR are considered as a subgroup of TEAE. An ISR that fulfills the criteria of an SAE will be documented and reported as such.

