4.6.2.1 Adverse Event

AEs will be summarized by presenting the number and percentage of patients having any AE, by SOC and PT.

In addition, the number of events will also be presented for any AE, by primary SOC and for each PT. The average rate of adverse events will also be calculated as the number of events divided by the total number of years of exposure.

Missing and /or incomplete dates for AEs are imputed in a manner resulting in the earliest onset during the study period (see [Appendix 1](#) for details), additionally taking into account that the start date should not be after the stop date. The maximum of the earliest possible start date and the date of first administration of investigational study medication will be imputed for missing dates. If the end date is prior to the date of first administration of investigational study medication then the AE is not considered as a TEAE.

AE summary will be provided for all study periods by treatment groups and for the entire study separately. Following data will be summarized in the overall AE summary presentation.

Total number of TEAEs, patients with at least one TEAE, at least one SAE, at least one treatment related TEAE, at least one severe TEAE, at least one treatment related SAE, patients who discontinued the study due to TEAE, patients requiring study drug interruption and number of patients who died.

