6.1.2 Adverse event start date

The algorithm only applies to event that has partial start date. Please note that **completely missing start dates** will not be imputed.

Note: Imputed dates will be used in the derivation of treatment emergent AEs and assignment of study periods. The actual partial dates will be reported in the listings.

The following matrix explains the logic behind the imputation.

	MON MISSING	MON < TRTM	MON = TRTM	MON > TRTM
YYYY < TRTY	(D) Before Treatment Start	(C) Before Treatment Start	(C) Before Treatment Start	(C) Before Treatment Start
YYYY = TRTY	(B) Uncertain	(C) Before Treatment Start	(A) Uncertain	(A) After Treatment Start
YYYY > TRTY	(E) After Treatment Start	(A) After Treatment Start	(A) After Treatment Start	(A) After Treatment Start

The following table is the legend to the logic matrix.

	Day	Month	Year
Partial Adverse Event Start Date	Not used	MON	YYYY
Treatment Start Date (TRTSTD)	Not used	TRTM	TRTY
Treatment in SP2 Start Date (TRT2STD)	Not used	TRT2M	TRT2Y
Relationship			
Before Treatment Start	Partial date indicates AE start date prior to Treatment Start Date		
After Treatment Start	Partial date indicates AE start date after Treatment Start Date		
Uncertain	Partial date insufficient to determine relationship of AE start date to Treatment Start Date		
Imputation Calculation			
NC / Blank	No convention		
(A)	MAX (01MONYYYY, TRTSTD)		
(B)	TRTSTD		
(C)	15MONYYYY		
(D)	01JULYYYY		
(E)	01JANYYYY		

In cases in the categories (A) and (E) when it is unclear due to the partial date if the AE started in SP1 or SP2 (YYYY = TRT2Y and MON=TRT2M in SP2) it will be considered to have started in SP2 and AE start date will be imputed as TRT2STD.

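### For patients treated across a New Year, the SAP imputes a year-only AE end in the first-dose year to before the first dose, and its TEAE rules then conflict.

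*SAP*

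**What the plan says.** **End dates.** For an AE end date with day and month missing, SAP 6.1.1 says to "impute the date with the day and month of the last available assessment date for the patient". The recorded year stays, and nothing stops the result falling before the AE start or the first dose. SAP 6.2.1 gives the same rule for concomitant medications.

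**Use of imputed dates.** SAP 2.1.2 states: "Imputed dates will be used for further derivations". The start-date section, 6.1.2, adds: "Imputed dates will be used in the derivation of treatment emergent AEs and assignment of study periods".

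**TEAE status.** SAP 4.6.2.1 says that if "the end date is prior to the date of first administration of investigational study medication then the AE is not considered as a TEAE". In the same paragraph, start dates are imputed "additionally taking into account that the start date should not be after the stop date". SAP 2.3.2.1, by contrast, defines a TEAE by its start after the first dose and treats an AE that cannot be classified as treatment emergent.

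**Medications.** SAP 4.3.3 counts a drug as prior only when its stop is unambiguously before the first administration. Where the data do not settle this, the drug is taken as not having ended before treatment.

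**Study period.** SAP 2.3.2.1 states: "If it is unclear whether the AE belongs to SP1 or SP2 then the AE will be assigned to SP2"; 4.1.2 agrees. In Appendix 1 (6.1.2) a year-only start in the first-dose year goes to the first dose date (category B), and one in a later year goes to 1 January (category E). The Study Period 2 override begins "In cases in the categories (A) and (E) when it is unclear due to the partial date" and requires both year and month to match the start of that period.

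**The concern.** The end-date rule borrows a day and month from one calendar year and attaches them to another. In a study lasting less than a year, that can move an event that ended on treatment back to before treatment began. A separate sentence then uses the end date to decide whether the event counts as treatment emergent. Comparing AE incidence between GP2017 and US-licensed Humira is a stated secondary objective, so a rule that reclassifies on-treatment events as pre-treatment bears directly on a planned output. It also runs against the SAP's own cautious intent elsewhere, where doubtful AEs count as treatment emergent and doubtful medications as concomitant.

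**Working it through.** The documents give no figure to reproduce, so this is a calendar check.

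**Inputs.** Week 48 is Day 337 (protocol Table 6-1), so the last scheduled visit is 337 − 1 = 336 days after the first dose. With the ±3-day window (SAP 4.1.4) it is at most 339. Week 24 is Day 169, or 168 days after. Week 12 is Day 85, or 84 days after.

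**Formula.** Let D be the first dose, L = D + f the last assessment, and Y the recorded end year. Imputed end = day and month of L in year Y.

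- *Y is the year of D, and L falls in the next year.* The imputed end is L moved back one year: D + f − 365, or D + f − 366 if the span contains a 29 February. This precedes D whenever f is 364 or less.
  - Week 48: 336 − 365 = −29, or 336 − 366 = −30 days.
  - Week 24: 168 − 365 = −197, or 168 − 366 = −198 days.
- *Y is the year of L.* The imputed end is L itself, which is not before D.
- *D and L in the same year.* The imputed end is again L.

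**Enumeration.** All 365 first-dose dates of a non-leap year were tried. A last assessment on 29 February has no counterpart in a non-leap year and was set to 28 February.

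| Last assessment | First-dose dates crossing 31 December | End in first-dose year imputed before D | End in last-assessment year imputed before D |
|---|---|---|---|
| Week 12 (84 days) | 84/365 = 23% | 84/84 | 0/84 |
| Week 24 (168 days) | 168/365 = 46% | 168/168 | 0/168 |
| Week 48 (336 days) | 336/365 = 92% | 336/336 | 0/336 |
| Week 48 + 3 days (339) | 339/365 = 93% | 339/339 | 0/339 |

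The second column is a share of possible start dates, not of events. As an assumption, spread first doses evenly over the year and true AE ends evenly over follow-up. Half of the on-treatment ends in crossing patients then fall in the first-dose year. The share of year-only ends misplaced is about 0.92 × 0.5 = 46% for Week 48 completers, 0.46 × 0.5 = 23% if follow-up stops at Week 24, and 0.23 × 0.5 = 11–12% at Week 12.

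**Example.** First dose 1 June 2016, Week 48 visit 3 May 2017, AE end recorded as 2016. The imputed end is 3 May 2016, 29 days before the first dose.

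- *Start also recorded only as 2016.* Category B sets it to 1 June 2016, which now follows the stop. The start-not-after-stop condition pulls it back, and the end-date sentence in 4.6.2.1 excludes the event.
- *Start recorded in full, say 1 July 2016.* SAP 2.3.2.1 makes it a TEAE and 4.6.2.1 says it is not. No order of precedence is given.

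**A safer rule in the same SAP.** For medical history, SAP 4.3.2 imputes a year-only stop as 31 December or, if the year is that of the first dose, as the last dose date. Neither can precede the first dose.

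**Year-only starts.** Category E means the month is missing, so an override that requires the month to match cannot apply. Category B has no override. Both sit badly with the rule that unclear AEs go to Study Period 2.

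**The case against.** The strongest reply is that the event is not necessarily lost. TEAE status in 2.3.2.1 rests on the start date, with a worst-case default. The end-date sentence in 4.6.2.1 stands in a paragraph about imputing onset, and the note in 6.1.2 on using imputed dates for TEAE status is in the start-date section. For an AE with a complete post-dose start this carries weight: the result is a contradiction, not a certain exclusion. It is weaker when both dates are partial, because the imputed dates then appear to settle the status and the worst-case default is not reached.

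Four stronger readings are tempting, and the documents do not support them:

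- **That on-study medications become prior ones and prohibited RA drugs are hidden.** SAP 4.3.3 largely protects against this, since a stop known only to the first-dose year is not unambiguously before treatment. The reset in 6.2.2 moves only imputed starts. RA medications are listed in full (4.3.3.1) and protocol deviations are reported separately (4.2). What remains is a conflict between 6.2.1 and 4.3.3.
- **That the error always reduces on-treatment records.** If first dose and last assessment fall in the same year, a drug stopped earlier that year, before the first dose, is moved to the last assessment date and looks on-study.
- **That negative durations will be reported.** SAP 4.1.3 leaves durations missing in the listings when the date is partial.
- **That 92% of year-only ends are affected.** That figure counts start dates.

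Materiality is also limited. AEs are sought at every visit, two-weekly in Study Period 1, and followed to resolution, so year-only ends should be rare. The primary and key secondary efficacy analyses do not use the rule.

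**Conclusion.** The end-date rule is wrong as written for one defined case: a patient treated across a New Year whose AE end is recorded only as the year of the first dose. There the imputed end precedes the first dose every time on the protocol schedule. This follows from follow-up of under one year and needs no assumption about recruitment. Loss of TEAE status follows on a literal reading of 4.6.2.1, most plainly when the start is also partial. With a complete post-dose start, the SAP contradicts itself.

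The 46%, 23% and 11–12% shares rest on even timing, because the documents give neither recruitment dates nor AE timing. The count of year-only ends is not given, so the effect on TEAE totals cannot be computed and is probably small. The correction is worth making because the rule is explicit, its result is wrong, and the repair is nearly free. The handling of year-only start dates is a separate inconsistency to reconcile.

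**What to change.** 1. **SAP 6.1.1 and 6.2.1:** impute a year-only end date as the earlier of 31 December of the recorded year and the last available assessment date, never before the recorded start. If the true end is on or after the first dose, both candidate dates are too, so none can be misplaced; the enumeration gave 0. In the example the imputed end becomes 31 December 2016.
2. **SAP 4.6.2.1:** exclude an AE as ended before treatment only if its observed end date, or its latest possible end date, precedes the first dose. An event that truly ended before the first dose in that year may then get a later imputed end, but a complete pre-dose start still keeps it from counting as newly started on treatment.
3. **SAP 6.1.2, separately:** reconcile year-only starts in categories B and E with the Study Period 2 rule in 2.3.2.1 and 4.1.2. Do not simply send every such AE to Study Period 2. That could take events out of the randomised Study Period 1 comparison, and an AE whose end date shows that it finished before Study Period 2 must stay in Study Period 1.

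The cost is a few sentences and a small programming change, with no new data. After database lock, SAP section 1 would require an addendum and an explanation in the study report.
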